**Background:** Undiagnosed and untreated depression is a significant cause of morbidity and mortality in low-middle-income countries (LMIC) such as India. The rates of diagnosis and treatment of depression among women in rural India are disproportionately low despite a primary care based task-sharing model of mental-health treatment. Stepped care approaches support appropriate treatment of symptoms while reducing the burden on healthcare systems and mobile technology can reduce the mental health treatment gap given its reach and easy access. However, as our preliminary study at a task-sharing care model in rural south India (Maanasi clinic, situated 60 miles from Bangalore city) revealed: illiteracy and the practice of sharing mobile phones as a family resource present hurdles to the adoption of mobile mental health (mHealth) based interventions. *To date, the feasibility of an mHealth application to screen depression, track symptom severity and support the delivery of stepped care treatment has not been tested in LMIC.*

**Specific Aim 1:** In phase I of this exploratory study, we will adopt a user centered participatory approach to design and develop a multiple-user, voice-response, mobile application (“MITHRA”), to be used in community-based organizations for screening, tracking and supporting stepped care treatment for depression, including select modules of the Healthy Activity Program, a brief psychological intervention based on behavioral activation. The application will include audio, video and enhanced touchscreen capabilities, to overcome the barrier of illiteracy and lack of access.

**Specific Aim 2:** In phase II, using a randomized-control design, we will examine feasibility and utility of “MITHRA” deployed at community-based organizations (n=3) vs enhanced usual care (n=3) in different villages supported by the Maanasi program (enrolling approximately 60 women).

**Specific aim 3:** Throughout the duration of the funding period we will arrange for mentored participation of Psychiatry and Community Medicine residents from India in the research project. Community Health workers will benefit from regular videoconference didactic and case presentation (ECHO) sessions such as symptoms of and treatment for common mental disorders.

The grant will accomplish the goals of developing a unique mobile application that is scalable, examining its feasibility and building research capacity at the research site in India.

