2. Depression measured by Quick Inventory of Depressive Symptoms (QIDS SR) at baseline 3 months and 6 months. QIDS SR will be collected by a blinded / masked research assistant. Research assessments will be conducted over the phone or in the Primary Health Center to avoid unblinding of CBO randomization status (presence of tablets in the CBOs)
3. Behavioral Activation – Behavioral Activation Depression Scale (BADS). We will administer the BADS to all women to calculate adherence to behavioral activation recommendations (for intervention women) and to measure degree of behavioral activation (for Enhanced Usual Care women).
4. Mental health services utilization – At baseline, 3 months and 6 months. We will obtain information on rates of utilization of mental health services including number of contacts with mental health providers and details of medications taken.

Depression – clinical outcome (not research measure)- Patient Health Questionnaire – 9. We will obtain information on rates of utilization of mental health services including the number of contacts with mental health providers and details of medications taken.

**5.5 Data sources.** For all types of data that will be accessed or collected for this research: Identify whether the data are being obtained from the subjects (or subjects' specimens) or whether they are being obtained from some other source (and identify the source).

*If you have already provided this information in Question 5.1, you do not need to repeat the information here.*

All research measures will be obtained from subjects by research coordinators in person or by phone.

**5.6 Identifiability of data and specimens.** Answer these questions carefully and completely. This will allow HSD to accurately determine the type of review that is required and the relevant compliance requirements. Review the following definitions before answering the questions:

**Access** means to view or perceive data, but not to possess or record it. See, in contrast, the definition of "obtain".

**Identifiable** means that the identity of an individual is or may be readily (1) ascertained by the researcher or any other member of the study team from specific data variables or from a combination of data variables, or (2) associated with the information.

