**10.8 Withdrawal of participants.** If applicable, describe the anticipated circumstances under which participants will be withdrawn from the research without their consent. Also, describe any procedures for orderly withdrawal of a participant, regardless of the reason, including whether it will involve partial withdrawal from procedures and any intervention but continued data collection or long-term follow-up.

Participants will be withdrawn from the trial in case of emergent suicidal ideation or new psychosis as they will be directed to a higher level of care.

**10.9 Anticipated direct benefits to participants.** If there are any direct research-related benefits that some or all individual participants are likely to experience from taking part in the research, describe them below:

*Do not include benefits to society or others, and do not include subject payment (if any). Examples: medical benefits such as laboratory tests (if subjects receive the results); psychological resources made available to participants; training or education that is provided.*

All participants will receive standardized depression education. Participants randomized to the intervention will receive the MITHRA intervention for the treatment of depression.

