**Statistical Methods:**

Assumptions of normality was assessed using Q-Q plot. Descriptive statistics, mean and standard deviation for normally distributed variables were used to describe the outcome parameters PHQ, QIDS. WHODAS and BADS. Chi-square test or Fisher's exact tests as appropriate, was used to test the association between baseline characteristics between study groups. At each time of assessment, outcome parameters were compared between study groups using independent t test or Mann Whitney U test as appropriate. Change in the outcome at 3 and 6 months from baseline was compared between the study groups using Wilcoxon signed rank test. McNemar Chi-square test was used to compare the change in the proportion of depression categories from baseline within each study group. In addition, RMANOVA was performed to compare the change in the outcome scores over time between study groups. A p-value of  $< 0.05$  was considered statistically significant. All analyses were performed using SPSS version 26.0.

---

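### RMANOVA as planned drops any woman with a missing visit and has no term for the randomized CBOs; a mixed model would keep every follow-up score

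*Combined protocol and SAP*

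**What the plan says.** The Statistical Methods section closes its list of tests, after the words In addition, with "RMANOVA was performed to compare the change in the outcome scores over time between study groups". It then names the software: "All analyses were performed using SPSS version 26.0". It gives no rule for missing visits, no imputation, no analysis population, no primary analysis and no term for the CBO, although section 5.1 randomizes three CBOs to the app and three to enhanced usual care.

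Two other between-arm comparisons are listed:

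- by visit: "At each time of assessment, outcome parameters were compared between study groups using independent t test or Mann Whitney U test as appropriate";
- for change: "Change in the outcome at 3 and 6 months from baseline was compared between the study groups using Wilcoxon signed rank test".

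Section 5.4 sets the visit schedule: "Depression measured by Quick Inventory of Depressive Symptoms (QIDS SR) at baseline 3 months and 6 months". Service use follows the same three visits. BADS has no stated times, and WHODAS is not listed in that section. Section 1.5 foresees "enrolling approximately 60 women". Section 10.8 states: "Participants will be withdrawn from the trial in case of emergent suicidal ideation or new psychosis". The form asks there whether data collection continues after withdrawal; the answer does not say.

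**The concern.** Standard repeated-measures ANOVA needs a full row of visits for each woman. That is a property of the method; the documents do not mention it, and I assume the usual SPSS procedure was meant. A woman with baseline and 3-month scores who misses month 6 is removed entirely, and both observed scores are lost.

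In a trial of about 60 women this costs precision. It can also cost validity. The protocol foresees withdrawal for a worsening mental state, so some 6-month scores may be missing for reasons linked to outcome. Detection may also differ by arm. Section 5.1 has app-arm women complete the PHQ-9 at CBO meetings, with an alert on the suicidal-ideation item, and describes no such in-meeting screening under enhanced usual care. Section 10.10 does apply follow-up of that item to all subjects.

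The missing CBO term is a second gap in the same analysis: women in one CBO are treated as independent although whole CBOs were allocated.

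**Working it through.** The documents give no dropout rate, standard deviation, correlation, effect size or sample-size derivation, so there is no planned figure to reproduce. Everything below except the 60 women, three visits and six CBOs is an assumption.

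**1. Women kept, if each follow-up visit is missed independently at rate d.** Complete cases = 60 × (1 − d)².

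- d = 10%: 60 × 0.81 = 48.6
- d = 20%: 60 × 0.64 = 38.4

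**2. Precision lost through deletion at 3 months.** The fair comparator is the women actually seen at 3 months, 60 × (1 − d), which is 54 or 48. The ratio of standard errors is the square root of (1 − d)/(1 − d)².

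- d = 10%: √(0.9/0.81) = 1.05
- d = 20%: √(0.8/0.64) = 1.12

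**3. If only month 6 is missed, by 10%, 20% or 30%.** RMANOVA drops 6, 12 or 18 women and, at two scores each, discards 12, 24 or 36 observed baseline and 3-month scores. The 3-month standard error rises by √(1/0.9) = 1.05, √(1/0.8) = 1.12 or √(1/0.7) = 1.20.

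**4. Bias, by simulation.** Settings: 30 women per arm, SD 1, correlation 0.5 between any two visits, true difference −0.50 at 3 and 6 months, only month 6 missing, 1,500 runs per scenario, Monte Carlo standard error about 0.007 to 0.008, no clustering. Each cell gives the complete-case estimate at 10% / 20% / 30% missing.

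| Missingness at month 6 | 3-month difference | 3-month change | 6-month change |
|---|---|---|---|
| Completely at random | −0.499 / −0.499 / −0.497 | −0.494 / −0.491 / −0.493 | −0.500 / −0.497 / −0.497 |
| Higher 3-month score more likely to be lost, both arms alike | −0.475 / −0.441 / −0.425 | −0.482 / −0.473 / −0.467 | −0.505 / −0.494 / −0.501 |
| The same in the app arm only, at random in the other | −0.584 / −0.673 / −0.741 | −0.539 / −0.587 / −0.627 | −0.490 / −0.511 / −0.507 |

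The change columns are closest to what an arm-by-time test uses. The distortion sits in the 3-month contrast. The 6-month change stays near −0.50 here because the assumed equal correlations shift baseline and 6 months alike, which need not hold in practice.

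Two alternatives recovered the truth in every scenario. The 3-month difference in all women seen at 3 months (the data for the planned per-visit test) and a likelihood model on all visits both gave −0.49 to −0.51. That model treated all three visits as responses with an unstructured covariance, so it supports the principle of the fix and not its exact form.

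**5. The CBO term.** With 60/6 = 10 women per CBO, the variance of a comparison at one visit is inflated by 1 + 9 × ICC. For assumed ICCs of 0.01, 0.05 and 0.10 this is 1.09, 1.45 and 1.90.

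**The case against.** The case against is substantial, and four stronger readings must be set aside.

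- **That the plan's 3-month comparison as a whole is biased.** A reader might infer this from RMANOVA's deletion. The per-visit t or Mann-Whitney test keeps a woman who misses month 6, so only RMANOVA's internal 3-month contrast is exposed. Missing 3-month scores could still affect the per-visit test, but that is another matter.
- **That RMANOVA is the only between-arm analysis of change.** The plan also compares change at 3 and 6 months separately, and the 3-month change needs only two scores. The signed rank test named for it is a paired test and cannot compare independent arms. That is a separate defect, though it leaves RMANOVA carrying more weight than an additional analysis should.
- **That standard errors rise by 11% to 25%.** √(1/0.81) = 1.11 and √(1/0.64) = 1.25 compare complete cases with no missing data at all, which no model can restore.
- **That the bias is about half a scale point.** Suppose the top 10% of 3-month scorers in one arm miss month 6 (SD 5, correlation 0.5). The 3-month mean then shifts by 5 × 0.1755/0.9 = 0.975, baseline shifts by half of that, and the change shifts by 0.49. The documents support no such pattern. Section 10.8 concerns suicidal ideation and psychosis, not total score, and it applies to both arms.

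It is also fair to say that this is a feasibility trial, that no primary analysis is named, and that the missing CBO term affects every listed test. What remains is that RMANOVA discards observed scores, no missing-data method is stated, and bias is possible if dropout relates to outcome.

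**Conclusion.** The point holds in limited form. RMANOVA as described loses every woman with an incomplete record and ignores the unit of randomization.

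- **Precision:** under an assumed 10% to 20% missing independently at each follow-up visit, about 49 to 38 of 60 women remain. The avoidable rise in the 3-month standard error is about 5% to 12%.
- **Bias in the 3-month change contrast:** none if data are missing completely at random. It is about 0.02 to 0.03 SD if score-related dropout is alike in both arms (10% to 30% missing at month 6), and about 0.04 to 0.13 SD if it occurs in one arm only. These sizes rest on the simulation's assumptions.

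Section 10.8 makes outcome-related missingness plausible but does not establish its rate or any difference between arms. The three-visit argument is documented for QIDS; for BADS and WHODAS it depends on schedules that section 5.4 does not give.

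**What to change.** Replace RMANOVA in the Statistical Methods section with a likelihood-based linear mixed model, which SPSS 26 can fit:

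- **Responses:** the 3-month and 6-month scores, using all available follow-up visits.
- **Fixed effects:** arm, visit, arm-by-visit and baseline score. Baseline enters as a covariate only, not also as a response.
- **Random effects:** intercepts for CBO and for woman, or a CBO intercept with an unstructured within-woman covariance.
- **Inference:** small-sample degrees of freedom reflecting six CBOs in two arms, so about 6 − 2 = 4 for the arm effect.

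State that validity rests on missing at random. Withdrawal triggered by worsening between visits could violate this, and the mixed model does not cure that. State also that a woman with no follow-up score, or no baseline score, does not contribute. Report missing visits by arm, visit and reason, and say whether outcome assessments continued after withdrawal.

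The cost is SAP wording and a different procedure in the same software, with no new data collection. Intervals will be wider because there are few CBO degrees of freedom. The section is written in the past tense, so if RMANOVA has already been run, this becomes a re-analysis. It should be labelled as such and reported beside the RMANOVA result.
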